8.2.3.5 End of study

- Visit date
- Discontinuation or continuation (if interruption, date of last administration, reason for interruption)
- The final efficacy evaluation
- NIS physician's electronic signature for data integrity

8.2.3.6 Follow-up period

Patients with adverse events noted at the final follow-up visit or upon premature discontinuation of JARDIANCE[®] will be monitored further until the resolution of those adverse events. Alternatively, those patients will be followed up until the NIS physician and sponsor agree that no further follow-up is necessary.

Proprietary confidential information © 2017 Boehringer Ingelheim International GmbH or one or more of its affiliated companies

8.2.4 Study discontinuation

Boehringer Ingelheim Korea reserves the right to discontinue the study overall or at a particular study site at any time for the following reasons:

- Emergence of any effectiveness/safety information that could significantly affect continuation of the study
- Violation of applicable local regulations, the NIS protocol, or the contract by a study site or participating physician, disturbing the appropriate conduct of the study.

8.3 VARIABLES

8.3.1 Analysis sets

A total of 3000 patients will be entered in this study, and each patient will be followed for total three times (baseline, short term 12weeks follow up, long term 24weeks follow up). Since T2DM is chronic disease it might be restrictive to collect safety and effectiveness data in short-term (12weeks) period, all patients will be enrolled for long-term (24weeks) surveillance.

8.3.1.1 Number of cases subject who entered the study

This number means the planned number of cases as specified in the contract concluded with the investigator (physician) prior to initiation of the study.

8.3.1.2 Number of cases subject to CRF collection

This number means the number of cases who signed the informed consent form to participate in the study as subject, with a record of taking JARDIANCE® once at least.

8.3.1.3 Number of cases subject to safety evaluation

These include those who signed the informed consent form to participate in this study as subject, took JARDIANCE® once at least, and were followed up by the physician once or more.

Reflecting Ministry of Food & Drug Safety (MFDS) guideline, the cases below shall be excluded from safety analysis (defined below) set in the following order:

- a. Patients who signed on the data release consent form of JARDIANCE® rPMS prior to the contract date
- b. Patients administrated JARDIANCE® prior to the contract date
- c. Patients administrated JARDIANCE® prior to the signed on the data release consent form
- d. Patients who have not taken JARDIANCE®
- e. Follow-up failure: Patients whose safety information can not be obtained due to follow-up Loss
- f. Patients who were prescribed for other indications except indications in the local label

Proprietary confidential information © 2017 Boehringer Ingelheim International GmbH or one or more of its affiliated companies

8.3.1.4 Number of cases subject to efficacy evaluation

These cases include those who signed the informed consent form to participate in this study as subject, visited as per the study schedule, took JARDIANCE[®], and were evaluated for the efficacy.

Reflecting Ministry of Food & Drug Safety (MFDS) guideline, the cases below shall be excluded from efficacy analysis (defined below) set in the following order:

- a. Patients excluded from safety analysis set listed in section 8.3.1.3
- b. Patients with missing information of assessment of efficacy set listed in section 8.3.2.2 at visit 2, visit 3.

8.3.2 Endpoints

8.3.2.1 Endpoints of safety

All reported adverse events in patients who take at least one dose of JARDIANCE® will be noted.

Endpoints pertaining to safety will be presented as incidence rates of adverse events and will include:

- Adverse events
- Unexpected adverse events
- Serious adverse events
- Drug-related adverse events
- Non serious adverse drug reaction
- Adverse event of special interest
- Adverse events leading to discontinuation

8.3.2.2 Endpoints of effectiveness

8.3.2.2.1 Main endpoint

Change from baseline in HbA1c after 12 weeks and/or 24 weeks of treatment

8.3.2.2.2 Other endpoints

- Occurrence of treat to target effectiveness response that is an HbA1c under treatment of < 7% after 12 weeks and/or 24 weeks of treatment
- Occurrence of relative effectiveness response (HbA1c lowering by at least 0.5% after 12 weeks and/or 24 weeks)
- Change from baseline in fasting plasma glucose (FPG) after 12 weeks and/or 24 weeks of treatment
- Change from baseline in body weight after 12 weeks and/or 24 weeks of treatment.
- Change from baseline in blood pressure (SBP, DBP) after 12 weeks and/or 24 weeks of treatment.

Proprietary confidential information © 2017 Boehringer Ingelheim International GmbH or one or more of its affiliated companies

8.3.2.2.3 The final efficacy evaluation

Records by performing the final efficacy evaluation at the end of the last visit

- ① Improved: If determined as there is any effect of maintaining or improving disease related factors.
- ② Unchanged: If disease related factors have not been changed compared with before administration, and not determined as there is any effect of maintaining symptoms.
- 3 Aggravated: If disease related factors are worse than before administration.
- 4 Unassessable: If it cannot be determined due to insufficient information collected. (Even though there are any objective indicators present, it is possible to belong to this grade.)

'Improved' is assessed as "Effective", "Unchanged" and "Aggravated "are assessed as "Invalid".

8.3.3 Assessment criteria

8.3.3.1 Assessment of safety

- Adverse events (event name/ symptoms/ sign/ identify hypoglycemia symptoms)
- Onset date, End date
- Intensity (Mild/ Moderate/ Severe)
- Serious (Serious/ Non-Serious)
- Outcome of the event (Recovered/ Recovering/ Not yet recovered/ Sequela/ Unknown)
- Causality (Certain/ Probable · Likely/ Probable/ Possible/ Unlikely/ Conditional · Unclassified/ Unaccessible · Unclassifiable)
- Factors other than JARDIANCE® (None/ Concomitant medication/ Concomitant disease/ etc)
- Action taken with study drug due to AE (Discontinued/ Reduced/ Increased/ Continue/ Unknown/ Not applicable)
- Recurrence in reintroduced (Recurrence/ Do not recur/ Unknown/ Not applicable)
- Adverse Event of Special interest (Not applicable/Vaginal moniliasis, vulvovaginitis, balanitis and other genital infection/Increased urination/Urinary tract infection/Volume depletion/ Diabetic Ketoacidosis, Decreased renal function, Hepatic injury defined by the alterations of liver parameters/Lower limb amputation)
- Investigator's comments(if needed)

8.3.3.2 Assessment of efficacy

① HbA1c:

HbA1c should be collected within 1 month prior to baseline and after 12 weeks and 24 weeks of treatment.

② Fasting Plasma Glucose (FPG):

FPG should be collected within 1 month prior to baseline and after 12 weeks and 24 weeks of treatment.

3 Body Weight:

Body weight should be collected within 1 month prior to baseline and after 12 weeks and 24 weeks of treatment.

Blood Pressure (SBP, DBP):

Blood pressure(SBP, DBP) should be collected within 1 month prior to baseline and after 12 weeks and 24 weeks of treatment.

S Final efficacy evaluation: Final efficacy evaluation should be accessed and recorded at the end of the last visit.

8.3.4 Items of Investigation

8.3.4.1 Demographic data

For demographic evaluation, following background information of subjects shall be recorded:

- Subject signed date
- Subject study number
- Age
- Gender
- Pregnancy (current status)
- Height
- Body weight
- Smoking status

8.3.4.2 Medical/Surgical history and pre-treatment experience

The medical/surgical history to be collected and the treatment experience prior to administration of this drug includes:

- Date of diagnosis
- Family history of T2DM
- Diabetes mellitus related complication (including but not limited to Retinopathy, Neuropathy, Nephropathy, Vasculopathy, etc.)

Proprietary confidential information © 2017 Boehringer Ingelheim International GmbH or one or more of its affiliated companies

• Medical history: Hypertension, Dislipidemia, Coronary artery disease, Stroke, Liver disease, Renal failure, Allergy, Nephropathy, etc.

8.3.4.3 Concomitant medication

Information on concomitant medication that is to be collected includes:

- Brand name or generic name
- Daily dose
- Unit
- Indication
- Start date
- Date of discontinuation or continuation

8.3.4.4 Drug administration status

Information on the study drug administration status includes:

- Dose
- Unit
- Start date
- Date of discontinuation or continuation

8.3.4.5 Information on the site

Information on the site includes:

- Hospital name
- Department
- Physician name

8.4 DATA SOURCES

This study will be carried out in the manner of successive survey that the investigator will be asked to successively write in the case report forms(CRFs) from the subject who was initially administered the drug following the study start date to the requested number of subjects without omission. Prior to initiation of the study, written contract shall be concluded, and this contract shall be concluded with the head of the site or the investigator with his/her consent.

8.5 STUDY SIZE

The sample size of 3,000 patients is based on the requirement of the local regulatory authority (MFDS). As per regulation, long-term surveillance is necessary for the T2DM indication. Since T2DM is chronic disease it might be restrictive to collect safety and effectiveness data in short-term (12weeks) period, all patients will be enrolled for long-term (24weeks) surveillance.

Proprietary confidential information © 2017 Boehringer Ingelheim International GmbH or one or more of its affiliated companies

8.6 DATA MANAGEMENT

Patients' data will be gathered by eCRF. The data management procedures to ensure the quality of the data are described in detail in the data management plan (DMP) available in TMF. Data management and statistics will be outsourced to a qualified contract research organization (CRO).

8.7 DATA ANALYSIS

8.7.1 Analysis of demographic data

Demographic data and the health status of subjects for the safety evaluation will be analysed descriptively. For continuous data, mean, standard deviation, minimum value, and maximum value will be described, while for categorical data, frequency will be shown.

Parameters corresponding to demographic data are as mentioned below.

- Basic information and disease information
 Age, gender, pregnancy, body weight, smoking status, diabetes mellitus
 complications, other medical history, disease period, Family history of T2DM,
 elderly (Age ≥ 65 years), renal impairment and hepatic impairment, allergy, long
 term use(over 24 weeks)
- ② Medication information Concomitant medication, study drug administration status (total period of drug use, average of daily dose), reason for early interruption, any anti-diabetic agents

To assess the extent of preferential prescribing and the potential for channeling bias, data from the TRAJENTA® (linagliptin) rPMS will be used as a comparator. The baseline characteristics of patients starting JARDIANCE® for the first time will be compared to the baseline characteristics of patients who started TRAJENTA® for the first time. Proportions and means (SD) of the baseline characteristics will be compared using absolute standardized differences (ASD), where an ASD of at least 10% will be considered a meaningful difference. p-values will also be calculated.

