8.1.3 Concomitant therapy, Restrictions, And rescue

Additional drugs are allowed as considered necessary for the patient's welfare to be prescribed at the discretion of the treating physician. It is required, however, to record the details in the eCRF of all concomitant medication administered to the patient during the course of treatment. This includes concomitant therapies started one month prior to JARDIANCE[®] initiation until the patient completes the final follow-up visit.

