8.7.2 Safety analysis

- ① Among the subjects of safety evaluation, the number of subjects with adverse event incurred and the number of adverse events incurred should be calculated, and the incidence rate of adverse events and the 95% confidence interval should be presented.
- ② The number and percentage of adverse events by type and category should be presented.
- 3 Analysis should be made using Chi-square test or Fisher's Exact test on the adverse event onset status by demographic data of subjects of safety evaluation.

Proprietary confidential information © 2017 Boehringer Ingelheim International GmbH or one or more of its affiliated companies

④ To estimate any factors that are thought to influence the analyzed incidence rate of adverse events, logistic regression analysis should be conducted, and for statistically significant parameters, the meaning should be described.

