8.7.3 Efficacy analysis

- Mean, standard deviation, minimum value, maximum value, and median of changes in glycosylated hemoglobin(HbA1c) and fasting plasma glucose(FPG), body weight, and blood pressure (SBP, DBP), which were measured at the last visit versus baseline, should be presented, and if there is difference before administration versus after administration should be analyzed using paired t-test.
- ② If there is difference in the change of glycosylated hemoglobin(HbA1c) according to demographic parameters mentioned in 8.7.1 should be analyzed using t-test or ANOVA(Analysis of Variance).
- The frequency and percentage of patients who had glycosylated hemoglobin(HbA1c) reaching less than 7% (target efficacy response rate) at the last visit should be calculated, and the frequency and percentage of patients with glycosylated hemoglobin(HbA1c) decreased by at least 0.5% at the last visit should be calculated.
- For final efficacy evaluation (improved, unchanged, aggravated, unassessable) and 'effective(improved)'/'ineffective(unchanged, aggravated)', the number and percentage of subjects should be mentioned. The final effectiveness evaluation of "Improved" will be classified as "Effective", "Unchanged" and "Aggravated" will be classified as "Ineffective". The effectiveness rate and its 95% confidence intervals will be estimated with exact method.
- ⑤ To estimate any factors that are thought to influence an effective ratio, logistic regression analysis should be conducted, and for statistically significant parameters, the meaning should be described.

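### Section 8.7.1 counts on-study variables as demographic parameters, so the factor tests on HbA1c change and, most naturally read, on adverse events can show spurious associations in either direction

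*Protocol*

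**What the plan says.** Protocol section 8.7.1 introduces its list with "Parameters corresponding to demographic data are as mentioned below" and gives two groups. The medication group reads "Concomitant medication, study drug administration status (total period of drug use, average of daily dose), reason for early interruption", followed by anti-diabetic agents. The basic-information group, otherwise made up of patient and disease characteristics, closes with long-term use, which contains the words "term use(over 24 weeks". Nothing in the section limits any item to its baseline value. Section 8.1.3 has concomitant drugs recorded from one month before initiation "until the patient completes the final follow-up visit".

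Two later sections turn the list into tests. Section 8.7.3 item 2 examines HbA1c change "according to demographic parameters mentioned in 8.7.1 should be analyzed using t-test or ANOVA(Analysis of Variance". Section 8.7.2 item 3 calls for a "Chi-square test or Fisher's Exact test on the adverse event onset status by demographic data of subjects of safety evaluation", without citing 8.7.1. Section 8.7.2 item 4 and section 8.7.3 item 5 add logistic regressions for AE incidence and for the effective ratio. They name no covariates, and the meaning of significant parameters is to be described.

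Section 8.3.4.1 is also headed as demographic data. Its list is shorter: consent date, study number, age, gender, pregnancy, height, body weight and smoking status. It has no duration, dose, interruption or medication item.

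**The concern.** A factor that is meant to explain an outcome should be fixed before the outcome can occur. Total period of use, average daily dose, reason for interruption and long-term use are not, and concomitant medication is not if it is counted to the last visit. For AEs, the outcome can produce the factor. For HbA1c change, the response can drive the dose. A significant p-value on such an item then says little about which patients are at risk or respond better, yet it would sit in the same table as age, gender and renal impairment. Safety monitoring is the primary objective, so a reader of the report could take a consequence of AEs for something that predisposes to them.

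**Working it through.** **Routes in the protocol's own text.**

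- *AE to duration and dose.* Section 8.3.2.1 has AEs leading to discontinuation as an endpoint. Section 8.3.3.1 records the action taken because of an AE, including discontinuation, reduction and increase.
- *AE to interruption reason.* A patient whose reason is an AE has had an AE by definition, so AE occurrence in that category is 100% and the test is circular.
- *AE to concomitant drug.* Section 8.7.2.1 records therapy for the event, and section 8.1.3 collects drugs up to the final visit.
- *Duration to AE.* Section 10.2 collects AEs until 30 days after last administration, so longer use gives more time to record one. This runs against the first route.
- *HbA1c response to dose.* Section 8.1.2 allows a higher dose in patients who need more glycaemic control, so average daily dose depends partly on the response being tested.

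**Size.** The protocol gives no AE, stopping or treatment rates, so there is no figure to reproduce. Only N = 3,000 (section 8.5) and the 24-week follow-up (168 days) come from the document. The other inputs below are assumptions.

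*Hand calculation, early stopping.* Suppose 20% have an AE (600 with, 2,400 without), and 30% of the former but 10% of the latter stop before 24 weeks. The counts are 180 stopped and 420 not, against 240 and 2,160.

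Odds ratio = (180 × 2,160) / (420 × 240) = 388,800 / 100,800 = 3.86. Inverted, for long-term use, this is 0.26.

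Chi-square = 3,000 × (388,800 − 100,800)² / (600 × 2,400 × 420 × 2,580) = 159.5.

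This is one chosen case, in which AE-driven stopping dominates.

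*Hand calculation, concomitant drug.* Suppose 60% take one anyway, and half of the AE patients without one receive one for the AE. The proportion among AE patients is 0.6 + 0.4 × 0.5 = 0.8.

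Odds ratio = (0.8/0.2) / (0.6/0.4) = 2.67.

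*Simulation across a range.* There were 1,000 replicates per scenario with exponential AE and stopping times over 168 days. AEs were counted to 30 days after last dose and tested by Pearson chi-square at two-sided 0.05. No factor affected AE risk. The 24-week AE risk was 10% or 20%, and stopping for other reasons 10% or 20%. Each row spans those four combinations; odds ratios are averages over replicates.

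| Share of AEs that stop the drug | Odds ratio, early stopping vs AE | Replicates rejected |
|---|---|---|
| 0% | 0.52 to 0.55 | 77% to 100% |
| 10% | 0.91 to 1.41 | 6% to 60% |
| 20% | 1.38 to 2.45 | 74% to 100% |
| 30% | 1.97 to 3.69 | 100% |

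With 60% background use and half of AEs treated, concomitant medication gave odds ratios of 2.67 to 2.74 and was rejected in every replicate. A factor fixed at baseline was rejected in 3.3% to 6.0% of replicates, close to the nominal 5%. The false associations therefore come from the choice of variable.

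No size was worked out for HbA1c change, because the documents give no response or titration rates.

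**The case against.** The strongest reply is that only the HbA1c test is tied to section 8.7.1 by name. For the AE test, demographic data could mean the baseline list in 8.3.4.1. That is a fair point. Section 8.7.1 is the list in the analysis chapter and says what the term covers, so it is the more natural reading, but the link is an inference. Two different lists under one name are themselves something to reconcile.

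The concomitant-medication window in 8.1.3 is a data-collection rule, and Visit 1 records prior drugs separately, so an analyst could use baseline values. This also stands. The fault is that 8.7.1 sets no limit.

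A reader might infer that the logistic regressions are wrong as specified. The documents do not support that. Items 4 and 5 name no covariates, and their choice may properly sit in the analysis plan. On-study items are permitted there, not required.

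A reader might also infer that the study's safety inference as a whole is compromised. It is not. Sections 8.7.2 and 8.7.2.1 require AE incidence with 95% confidence intervals, overall and by preferred term, and these do not depend on the factor list.

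Finally, the regulator may want these analyses. The log in section 14 attributes the logistic regression to MFDS comments. Nothing in the protocol says that on-study variables must be tested, and the change below keeps the regressions and the tabulations.

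**Conclusion.** The point holds in a limited form. Section 8.7.1 mixes baseline and on-study variables. Section 8.7.3 item 2 tests HbA1c change against that list expressly, and 8.7.2 item 3 most naturally does the same for AEs. Some of these tests are circular and others can reflect the outcome acting on the factor. For HbA1c the main route is response-driven dose change rather than AEs.

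The direction is not fixed. A reader might infer that the report will show long-term use as protective, but under the assumptions above the odds ratio for early stopping lay on either side of 1 (about 0.5 to 3.7), and near 10% AE-driven stopping the two effects partly cancel. The actual bias in this study cannot be derived from the documents.

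Two further inferences should not be drawn. A family-wise error computed by treating the listed parameters as independent would mislead, because the list overlaps itself (age with elderly status, total period with long-term use). Nor is it shown that the 24-week cut misclassifies completers: Visit 3 is placed after 24 weeks, and the form records whether the drug continues.

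What is at stake is the interpretation of the factor tables. The AE incidence estimates are not affected.

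**What to change.** - Reconcile sections 8.3.4.1 and 8.7.1 so that demographic data has one meaning.
- Split 8.7.1 into baseline covariates and on-study descriptors.
- Limit the tests in 8.7.2 item 3 and 8.7.3 item 2 to variables fixed at or before first dose, with concomitant and anti-diabetic medication taken as recorded at Visit 1.
- State the same limit for the logistic regressions in 8.7.2 item 4 and 8.7.3 item 5.
- Tabulate total period of use, average daily dose, interruption reason, long-term use and on-study medication descriptively, without tests.
- If a relation between AEs and exposure is wanted, report events per patient-time.

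No new data are needed, since the baseline items are already collected at Visit 1. A few p-values leave the report tables, and the revised wording goes to the regulator with the protocol.

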8.2.2 Study population

8.2.2.1 Main diagnosis for study entry

Patients diagnosed with T2DM will be included.

8.2.2.2 Inclusion criteria:

- Patients who have started at first time on JARDIANCE[®] in accordance with the approved label in Korea
- Age ≥19 years at enrolment
- Patients who have signed on the data release consent form

8.2.2.3 Exclusion criteria:

- Known hypersensitivity to empagliflozin or any of its excipients
- Patients with type 1 diabetes or for the treatment of diabetic ketoacidosis (DKA)
- Patients with persistent eGFR<60 mL/min/1.73 m², end stage renal disease or on dialysis
- Patients with rare hereditary conditions of galactose intolerance, the Lapp lactase deficiency or glucose-galactosemalabsorption
- Patients for whom empagliflozin is contraindicated according local label of JARDIANCE[®]

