8.9.2 Channeling bias

Channeling bias can occur due to preferential prescribing in relation to different risks for the events of interest: e.g., if empagliflozin would be more often prescribed to higher risk patients compared to other treatments, higher incidences of outcome events were then expected in the empagliflozin group. To assess the extent of preferential prescribing of JARDIANCE® and the potential for channeling bias, baseline data from the TRAJENTA® (linagliptin) rPMS will be used to provide context for the JARDIANCE® rPMS data.

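### The channeling check sets a renally restricted JARDIANCE cohort against TRAJENTA starters of unstated eligibility, so the 10% ASD rule can flag renal differences that do not reflect prescriber preference

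*Protocol*

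**What the plan says.** Section 8.7.1 sets out the comparison. Its purpose is given as "To assess the extent of preferential prescribing and the potential for channeling bias", and "data from the TRAJENTA® (linagliptin) rPMS will be used as a comparator". The groups, new starters of each drug, are defined in one sentence: "The baseline characteristics of patients starting JARDIANCE® for the first time will be compared to the baseline characteristics of patients who started TRAJENTA® for the" (cut short here). ASDs are used to compare proportions and means, "where an ASD of at least 10% will be considered a meaningful difference", and p-values are added. The baseline parameters listed in the same section include "renal impairment and hepatic impairment, allergy", together with age, elderly status and diabetes complications.

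The exclusion criteria in Section 8.2.2.3 remove from the JARDIANCE cohort "Patients with persistent eGFR<60 mL/min/1.73 m², end stage renal disease or on dialysis" and also "Patients for whom empagliflozin is contraindicated according local label of JARDIANCE".

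Section 8.9.2 repeats the plan under limitations: "To assess the extent of preferential prescribing of JARDIANCE® and the potential for channeling bias, baseline data from the TRAJENTA® (linagliptin) rPMS will be used", there described as giving context. The direction it worries about is empagliflozin going to higher-risk patients.

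Neither 8.7.1 nor 8.9.2 gives the entry criteria of the TRAJENTA rPMS, applies the JARDIANCE criteria to its patients, or sets aside differences on variables that the entry criteria define.

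**The concern.** The comparison is meant to show whether physicians prefer one drug for certain kinds of patient. The JARDIANCE side, however, is filtered after the prescribing decision. A patient started on the drug despite persistent eGFR <60 cannot be enrolled, so the enrolled cohort carries no information about prescribing in that group. If the label also bars such patients, their absence reflects the label and still not discretionary choice.

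If the TRAJENTA rPMS admitted these patients, a renal difference between the cohorts would appear without any preference, and the 10% rule would report it under the heading of preferential prescribing. On renal status the distortion makes JARDIANCE users look lower-risk, which works against detecting the direction named in 8.9.2. This is the only channeling check in the protocol.

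**Working it through.** The plan has no derived figure to reproduce here: 10% is a chosen threshold, and the 3,000 patients in Section 8.5 are a regulatory requirement. The check asks how large an eligibility mismatch is needed to reach the threshold when prescribing is identical.

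**Inputs**
- From the protocol: the threshold of 0.10 (8.7.1), the renal exclusion (8.2.2.3), renal impairment as a listed parameter (8.7.1), and 3,000 JARDIANCE patients (8.5).
- Assumed, because the protocol does not give them: the TRAJENTA renal case mix, the eGFR distributions, the correlation of age with eGFR, and a TRAJENTA cohort of 3,000.

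**1. The excluded category itself**

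For proportions, ASD = |p1 − p2| / sqrt([p1(1−p1) + p2(1−p2)]/2). With 0 in JARDIANCE and p in TRAJENTA this becomes sqrt(2p/(1−p)). Setting it to 0.10 gives 2p/(1−p) = 0.01, so p = 0.01/2.01 = 0.0050.

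| TRAJENTA share p | ASD |
|---|---|
| 0.25% | 0.07 |
| 0.5% | 0.10 |
| 1% | 0.14 |
| 2% | 0.20 |
| 5% | 0.32 |
| 10% | 0.47 |
| 20% | 0.71 |

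**2. A broader renal impairment variable**

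Suppose JARDIANCE keeps a share m of mild or non-persistent cases, and both drugs draw on the same source population, of which a share e is excluded from JARDIANCE only. The TRAJENTA share is then e + (1−e)m. Solving ASD = 0.10 for e:

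| m in JARDIANCE | e needed |
|---|---|
| 2% | 1.7% |
| 5% | 2.5% |
| 10% | 3.6% |
| 20% | 5.2% |

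For m = 2%, for example, the TRAJENTA share is 0.0169 + 0.9831 × 0.02 = 0.0366. The ASD is 0.0166 / sqrt((0.0196 + 0.0352)/2) = 0.10.

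**3. Mean eGFR, same source population, JARDIANCE side truncated at 60 (normal distribution)**

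| Assumed mean/SD | Share below 60 | ASD |
|---|---|---|
| 85/20 | 10.6% | 0.22 |
| 90/20 | 6.7% | 0.15 |
| 95/20 | 4.0% | 0.09 |
| 100/20 | 2.3% | 0.06 |

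Mean eGFR is not named among the 8.7.1 parameters, and eGFR is recorded only if available (8.2.3.2). This table is therefore illustrative.

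**4. Spill-over to age**

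With an assumed correlation of −0.3 to −0.5 between age and eGFR, and source means of 85 to 100 (SD 20), the ASD for age is 0.02 to 0.10. Most of this range lies below the threshold.

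**5. The accompanying p-values**

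With an assumed 3,000 per group, p < 0.05 is reached at an ASD of 1.96 × sqrt(2/3000) = 0.051. The p-values therefore cannot separate an eligibility effect from a prescribing effect.

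**6. With aligned criteria**

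If both cohorts come from the same source population and the same exclusion is applied to both, the ASD produced by the exclusion is 0.

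**The case against.** The strongest objection is that the comparator's composition is unknown. A reader might infer that JARDIANCE patients are set against all first-time TRAJENTA users. The protocol does not say so: the comparator is the TRAJENTA rPMS, a separate study with criteria of its own. If those include the same renal exclusion, the artefact from this criterion disappears. That stands, and it makes the point conditional. It does not remove it, because without those criteria nobody can interpret the renal ASDs.

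A second objection is that filtering an external data set is a matter for the statistical analysis plan, which is not available here and may contain such a step. But the protocol itself fixes the groups, the threshold and the purpose, and those three together create the problem.

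Third, Section 8.9.2 can be read as concerned with cohort-level risk, for which comparing the cohorts as treated is informative. That is a good reason to keep the unrestricted comparison. It does not justify reading it as evidence of preferential prescribing, the purpose given in both sections.

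Fourth, the JARDIANCE share need not be 0%. Only persistent eGFR <60 is excluded, Section 8.3.1.3 does not list this criterion among the safety-set exclusions, and Section 8.2.2.4 anticipates patients with renal impairment. This stands, and it is why the 1.7% to 5.2% range is shown beside the 0.5% figure.

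Finally, the consequences are limited. The data serve as context, directions are visible from the proportions and means, and a careful reader could trace a renal gap to the exclusion list. This also stands.

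**Conclusion.** The point holds in a conditional form. As written, the 10% rule can report a difference in eligibility as a difference in prescribing for renal variables, unless the TRAJENTA rPMS carried the same renal exclusion. The mismatch needed is small: about 0.5% of TRAJENTA patients in the excluded category if JARDIANCE has none, or an excluded share of about 1.7% to 5.2% if a broader renal variable leaves 2% to 20% in JARDIANCE. These thresholds follow from the ASD formula; whether they are met depends on a case mix that the protocol does not give.

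Two wider readings are tempting and not supported. One is that the exclusion would distort age, diabetes duration and cardiovascular history as well, or mask channeling in general. The only such spill-over calculated, for age, is mostly below 0.10, and because ASDs are computed variable by variable, masking is shown only for renal status. The other is that the safety results are biased. Adverse event incidence is estimated within the single arm (8.7.2), and no estimate depends on these ASDs. The matter is worth correcting because the remedy is cheap, but it does not threaten the primary objective.

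**What to change.** In Sections 8.7.1 and 8.9.2:

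- State the eligibility criteria of the TRAJENTA rPMS.
- Compute the ASDs a second time after applying to the TRAJENTA cohort those JARDIANCE entry criteria that its data can evaluate: at least age ≥19, first use, and renal status where recorded. Give a rule for missing eGFR and for how persistence is judged.
- Base statements about preferential prescribing on this aligned comparison, and keep the unrestricted one as a description of how the cohorts differ.
- State that differences on variables defined by the entry criteria are not read as channeling.

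The cost is a few sentences, one filter and a second set of ASDs. The aligned comparator will be somewhat smaller, and the step depends on which renal data the TRAJENTA rPMS recorded. If those data are not usable, the protocol should say that renal differences cannot be interpreted as channeling. If the criteria already match, the addition does no harm.
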